4.2 Study Procedures

4.2.1 Hepatitis C Diagnosis and Recruitment Screen

Prior to study roll out, site investigators will meet with drug treatment center leadership to outline procedures for offering study participation to drug center clients. The OTP will facilitate HCV antibody testing and/or HCV RNA testing through rapid testing or phlebotomy. Prior to study enrollment, participants will complete an initial screening questionnaire, which will explore if the participant has previously been diagnosed with HCV, and if previously diagnosed, previously treated for HCV with oral direct-acting antiviral (DAA) therapy. Individuals who report previous HCV treatment with oral DAA therapy will not be eligible for study enrollment. Potential participants will also be asked about their current medications to ensure they are not currently taking any medication prohibited by the study (see Sections 5.1 and 5.3). Individuals who report taking a study-prohibited medication will not be eligible for study enrollment. These screening questions will be mixed with other questions to ensure that participants remain unaware of study eligibility criteria. Individuals who are HCV antibody or HCV RNA positive on testing and remain study eligible after completing the screening questionnaire will be offered enrollment into the study and if willing, go through the process of informed consent.

4.2.2 Informed Consent

Each participant must give consent according to local requirements after the nature of the study has been fully explained. The informed consent form (ICF) that is used must be approved by the Institutional Review Board (IRB) and be in a language that the participant can read and understand. The informed consent should be in accordance with principles that originated in the Declaration of Helsinki, current International Conference for Harmonization (ICH) and Good Clinical Practice (GCP) guidelines and applicable regulatory including IRB policy and requirements.

The participant will be given sufficient time to read the ICF and the opportunity to ask questions. After this explanation and before entry into the study, consent should be appropriately recorded. After having obtained the consent, a copy of the ICF must be given to the participant.

4.2.3 Demographic and Medical History

After signing consent, participant's name, date of birth, age (calculated), sex, primary and secondary forms of contact, address, race, and ethnicity will be collected. Medical history will be collected by participant interview. Participants will be asked to provide all medical history to the best of their recollection, and then will be asked specifically about the following medical history items that impact

eligibility: Presence of liver cirrhosis or history of decompensated liver disease or liver cancer, pregnancy, previous HCV treatment with oral DAAs, history of hepatitis B infection.

4.2.4 Concomitant Medication Documentation

All concomitant medications and supplements as of Day 0 will be recorded.

4.2.5 Pregnancy Test

All participants will be asked to provide information determining childbearing status. Females who are post-menopausal (absence of menses for 12 months or greater) or who have had a hysterectomy are considered not to be of childbearing potential. Any females not meeting these criteria are considered to be of childbearing potential and will have a point of care dipstick urine or serum beta human chorionic gonadotropin (HCG) test performed. Pregnant women will not be enrolled in this study.

Females of childbearing potential will be cautioned against getting pregnant or attempting to get pregnant during this study. Requirements for ongoing contraception are noted in protocol section 5.2.

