5 STUDY ACTIVITIES

5.1 Inclusion and exclusion Criteria

Inclusion criteria: Participants must meet all of the following inclusion criteria to be eligible for participation

- ✓ Ability and willingness of participant to provide written informed consent
- ✓ Men and women age ≥ 18 to ≤ 70 years at study entry
- ✓ HCV antibody positive/Detectable HCV RNA
- ✓ HCV treatment naïve (no prior treatment with an approved or investigational oral DAA therapy)
- ✓ Negative pregnancy test at screening or at the day of treatment initiation (females of childbearing potential only)
- ✓ If co-infection with Human Immunodeficiency Virus (HIV) is documented, the subject must be anti-retroviral treatment (ART) naïve with CD4 T cell count >500 cells/mm³ OR on a stable ART regimen (containing only permissible ART – Raltegravir; dolutegravir; Rilpivirine; Elvitegravir/cobicistat; Tenofovir disoproxil fumarate; Tenofovir alafenamide; Emtricitabine; Lamivudine and/or Abacavir, bicitegravir)

Exclusion criteria: Subjects who meet any of the following exclusion criteria are not to be enrolled in this study

- ✓ Women who are pregnant or breastfeeding, or considering becoming pregnant during the study and for 30 days after the last dose of study drug
- ✓ Known allergy/sensitivity or any hypersensitivity to components of study drugs or their formulation
- ✓ Current or history of decompensated liver disease (including but not limited to encephalopathy, variceal bleeding, or ascites) prior to study entry

- ✓ History of hepatocellular carcinoma (HCC)
- ✓ Any history of active Hepatitis B or positive HBsAg test
- ✓ Platelet count < 150,000/mm³
- ✓ HCV RNA undetectable
- ✓ History of clinically significant abnormalities or co-morbidities that make the subject an unsuitable candidate for this study, in the opinion of the investigator.
- ✓ Women of childbearing potential that are not practicing at least one specified method of birth control (refer to Section 5.2) that is effective from Study Day 1 through at least 30 days after the last dose of study drug.
- ✓ Subject is currently taking any of the following prohibited medications:
 - Red yeast rice (monacolin K), St. John's Wort
 - Carbamazepine, Dabigatran, efavirenz, phenytoin, pentobarbital, phenobarbital, primidone, rifabutin, rifampin
- ✓ Subject is not able or willing to safely discontinue the prohibited medications or supplements listed below at least 14 days prior to the first dose of GLE/PIB:

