5.2 Contraception Recommendations

Contraception Requirements for Females:

Postmenopausal is defined as:

- Age > 55 years with no menses for 12 or more months without an alternative medical cause.

If female, subject must be either post-menopausal, permanently surgically sterile (bilateral oophorectomy, bilateral salpingectomy or hysterectomy) or a woman of childbearing potential (WOCBP) and must practice at least one of the following methods of birth control, throughout the study including 30 days after the last study drug dose is given.

- Contraceptives and/or hormonal replacement therapies containing only progestins (such as those containing norethindrone, desogestrel, or levonorgestrel) or those containing progestins

with non-ethinyl estradiol estrogens (e.g., esterified or conjugated) associated with inhibition of ovulation initiated at least 1 month prior to study Baseline Day 1.

- Bilateral tubal occlusion/ligation.
- Intrauterine device (IUD).
- Intrauterine hormone-releasing system (IUS).
- Vasectomized sexual partner(s) (the vasectomized partner(s) provided the vasectomized partner has received medical assessment of the surgical success and is the sole sexual partner of the trial participant).
- Male or female condom with or without spermicide.
- Cap, diaphragm or sponge with spermicide.
- A combination of male condom with either cap, diaphragm or sponge with spermicide (double barrier method).
- True abstinence: Refraining from heterosexual intercourse when this is in line with the preferred and usual lifestyle of the subject, (periodic abstinence [e.g., calendar, ovulation, symptothermal, post-ovulation methods] and withdrawal are not acceptable).

For male study subjects no contraception is required.

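### Minor inconsistency: Sections 4.2.5 and 5.2 define post-menopausal differently, so a woman bound by the contraception rule can be exempt from the pregnancy test

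*Combined protocol and SAP*

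**What the plan says.** Section 4.2.5 decides who has a pregnancy test. It first states that "All participants will be asked to provide information determining childbearing status". It then sets aside, as not of childbearing potential, "Females who are post-menopausal (absence of menses for 12 months or greater) or who have had a hysterectomy". Everyone else falls under the next rule: "Any females not meeting these criteria are considered to be of childbearing potential and will have a point of care dipstick urine or serum" beta HCG test. For ongoing contraception, and only for that, 4.2.5 refers to Section 5.2.

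Section 5.2 has its own definition of postmenopausal: "Age > 55 years with no menses for 12 or more months without an alternative medical cause". A female participant must meet that definition, or be "permanently surgically sterile (bilateral oophorectomy, bilateral salpingectomy or hysterectomy) or a woman of childbearing potential (WOCBP"), and a woman in this last group must use a listed method of birth control.

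Section 5.1 uses the category of childbearing potential twice. One inclusion criterion is "Negative pregnancy test at screening or at the day of treatment initiation (females of childbearing potential only"), with no pointer to a definition. One exclusion covers "Women of childbearing potential that are not practicing at least one specified method of birth control (refer to Section 5.2"), which does point to 5.2. The eligible age range is 18 to 70.

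The schedules place the test at Day 0 (Appendix A) and at the Week 24 rescreen of standard of care participants for rollover (Appendix B). The footnotes, e in Appendix A and c in Appendix B, limit it to participants of childbearing potential and do not define the term.

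**The concern.** The two sections sort women into the same category by different rules, and the rule that decides testing is the looser one. The protocol can therefore require a woman to use contraception because she might conceive, yet exempt her from the test because she supposedly cannot. The 5.2 wording itself recognises that 12 months without menses does not always establish menopause, since it adds an age limit and asks about other causes.

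At stake is a confirmatory pregnancy test before study drug is given on site, and consistent practice across five sites that may resolve the conflict differently. This is a matter of eligibility and safety wording. It does not touch the primary endpoint, the sample size or the analysis.

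**Working it through.** No arithmetic applies to the definitions, and the plan gives no figure to reproduce. The check sets the two rules side by side for a woman who is not surgically sterile under 5.2 and has had at least 12 months without menses.

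| Case | Age | Other medical cause | 4.2.5 | 5.2 | Result |
|---|---|---|---|---|---|
| a | Over 55 | No | Not tested | Postmenopausal | Agree |
| b | Over 55 | Yes | Not tested if the parenthesis is taken literally | Childbearing potential | Conflict on the literal reading only |
| c | 55 or younger | No | Not tested | Childbearing potential | Clear conflict |
| d | 55 or younger | Yes | Not tested if the parenthesis is taken literally | Childbearing potential | Conflict on the literal reading only |

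These are cases under the rules. They say nothing about how often each occurs.

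**Can such women enrol?** Yes. The 18 to 70 age range admits all four cases.

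**Does another passage settle which definition governs the test?** No. The 5.1 test criterion cites neither section, the two schedule footnotes only repeat the term, and 4.2.5 hands only contraception to 5.2. If 5.1 is read with 5.2, the woman in case c lacks a required negative test. If 5.1 is read with 4.2.5, the criterion is met, but the two sections still contradict each other.

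**Which tests are lost?** Appendix A schedules one pregnancy test, at Day 0, and none at Treatment Day 1. In the test-and-treat arm the Day 0 test is therefore the only scheduled one before on-site drug. In the standard of care arm, Day 0 leads to off-site referral. For a woman who later rolls over, the test that precedes on-site drug is the Week 24 rescreen in Appendix B. The gap is one pre-drug test per affected woman treated on site, in either arm.

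**What still protects her?**
- The contraception rule in 5.1 and 5.2.
- The exclusion in 5.1 of "Women who are pregnant or breastfeeding, or considering becoming pregnant during the study and for 30 days after the last dose of study drug".
- The medical history question on pregnancy in 4.2.3.
- The question on childbearing status in 4.2.5.
- The condition in 4.2.9 that she is not pregnant when eligibility is confirmed at the treatment initiation visit.

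None of these orders the missing test.

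**Does the mismatch run the other way?** Yes, without harm. Section 5.2 counts bilateral oophorectomy and bilateral salpingectomy as sterile. Section 4.2.5 names only hysterectomy, so such a woman may be tested unnecessarily.

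**The case against.** The best defence is that the two definitions have separate jobs. Section 4.2.5 is headed as the pregnancy-test section, states its own rule for testing, and sends the reader to 5.2 for contraception only. In 5.1, only the contraception exclusion cites 5.2. On that reading the protocol deliberately applies a stricter rule to contraception than to testing, and a site that follows 4.2.5 complies with 5.1.

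Part of this stands. A reader might infer that 4.2.5 leads sites to enrol women in breach of 5.1. The documents do not support that, because the test criterion names no definition. What the defence does not explain is why the same term, feeding two criteria in the same list, should carry two meanings without a word to say so.

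A second objection is that 4.2.5 exempts women who are post-menopausal, with the 12 months only in parentheses. A woman whose periods stopped for another medical reason is not post-menopausal in the ordinary sense, and a site could reasonably test her. This also stands: cases b and d depend on reading the parenthesis as the whole definition. Case c does not.

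A reader might also count two missed tests for a standard of care participant, at Day 0 and Week 24. Both would be skipped, but the Day 0 test in that arm precedes a referral, not on-site dispensing, so it does not widen the gap before on-site drug.

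Finally, a reader might infer that women will be treated while pregnant, or harmed. The documents do not show this. The safeguards listed above remain, use is on-label (6.2.1), and 6.2.4 allows drug to continue at the Principal Investigator's discretion if pregnancy is found on treatment.

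**Conclusion.** The inconsistency is real and minor. The two sections plainly differ, and case c is a contradiction on any ordinary reading. The alternative-cause cases join it only if the parenthesis in 4.2.5 is taken literally, and the 5.1 criterion is unmet only if it is read with 5.2.

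The size is one missing confirmatory test before on-site GLE/PIB per affected woman, and only at a site that applies 4.2.5 as written. A site that reads 5.2 into 4.2.5 would test her. The number of women cannot be estimated, because the documents give no mix of sex, age or menstrual history. The primary analysis is unaffected.

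**What to change.** Give 4.2.5 the 5.2 definition. A female is not of childbearing potential if she is over 55, has had at least 12 months without menses and has no other medical cause for this, or if she has had a hysterectomy, bilateral salpingectomy or bilateral oophorectomy. Then have three places point to it: the negative-test criterion in 5.1, Appendix A footnote e and Appendix B footnote c.

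Aligning 5.2 to 4.2.5 would also remove the contradiction, but it would loosen the contraception rule. The documents do not show which definition was meant for testing. The stricter one is the cautious choice and leaves contraception as it is.

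The cost is wording, approval by the IRB or ethics committee (8.1) and distribution to sites (8.4.1), so it can wait for the next amendment. Each affected woman would have an extra urine dipstick at visits already scheduled: one in the test-and-treat arm (Day 0), and at most 1 + 1 = 2 in the standard of care arm (Day 0, plus Week 24 if rescreened). The total cannot be estimated. Women with bilateral oophorectomy or salpingectomy would no longer be tested, which the sponsor should accept knowingly.

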4.2.6 Vital Signs

Height, weight, temperature, pulse, respiratory rate and blood pressure will be collected at the study site.

4.2.7 Patient Reported Outcomes (PRO) and Quality of Life (QOL) Measures

We will utilize validated measures to assess patient reported outcomes and will also qualitatively assess satisfaction with HCV care received in both intervention and SOC arms. We will utilize the validated Eq 5d-5I¹⁶, validated PHQ-8¹⁷, GAD-7¹⁸, AUDIT C¹⁹, modified addiction severity index, MOS social support scale, Health efficacy and HCV stigma scales. We will also qualitatively assess participant perception of their HCV care among a purposively sampled group of patients who did and did not initiate HCV treatment in intervention (n=20) and standard of care (n=20) across the five OTPs. Participants will be offered interviews starting approximately 6 months post-randomization. In-depth interview guides will be designed to focus on experiences with HCV treatment, barriers and facilitators of HCV treatment initiation and completion.

4.2.8 Randomization

Randomization will occur separately at each OTP. Randomization will take place on day 0 after recruitment screening activities have been performed and the Investigator or designee has determined that the participant is eligible based on information that is available. Day 0 laboratory tests including blood HCV RNA, complete blood count (CBC), comprehensive metabolic panel (CMP), hepatitis B surface antigen (HBsAg), and urine/serum beta HCG, may not be available at the time of randomization and participants may be randomized without this information. Randomization will be built into the study REDCap database. It may not be known at screening whether participants have detectable HCV RNA or not. All participants will be randomized in a 1:1 ratio to test and treat strategy or standard of care referral. Participants who are found to have an HCV RNA that is not detectable, HbsAg positive or a platelet count that is <150,000 will not continue in the study, and will be referred to an offsite location for care.

4.2.9 Study Arms

Intervention – Test and Treat strategy: This will consist of a meeting (in person, by phone or over video) with a trained peer mentor who will meet with the study participant after randomization to communicate information about HCV in a manner that takes into account an understanding of experiences with HCV and care access faced by people who use drugs, the potential harms of untreated HCV and the benefits of HCV treatment.

Peer Training, Monitoring, and Quality Assurance. Peers will receive training modelled on our previous experience training peers for HCV treatment support. The training will be provided as modules. Topics to be addressed in the modules are: 1) Power of peer mentoring and key values including confidentiality and respect for all persons; 2) Tools for effective communication; 3) HCV disease and substance use disorder including importance of adherence to medications/visits; 4) Self-care in the peer-mentor role; 5) review of patient tracking tools. Peers will also have an individual training session. Individual sessions will prepare the peer for their peer support role including building communication skills to enhance conversations to support HCV care engagement. Peers will be trained to improve their communication skills with a focus on: 1) providing accurate information; 2) working with patients on goal setting for HCV treatment adherence; and 3) identifying barriers to retention in care. We will ensure peers have demonstrated competency in all of their tasks through knowledge and performance assessments as judged through role-plays.

Peer support and care coordination tasks. Peers will be responsible for maintaining contact with patients in the test and treat arm. They will also complete adherence and food use with medication surveys at weekly contacts. He or she will also communicate the need to return for results of follow up testing and follow through with recommended treatment. The Peer will also communicate to the patient the expected timing of follow up appointments at the drug treatment center and will offer support for the duration of HCV treatment. Up to 15 peers will be enrolled in this study.

The treatment initiation visit at the drug treatment center will depend on the standard amount of time it takes to get results of laboratory testing back to the drug treatment center site. We expect this to be 3-5 days.

The peer will contact the patient 2 days before and the day before the scheduled appointment to remind that participant about the appointment.

Peers will have a standard protocol for at least weekly phone contact with participants through post-treatment week 12, and will be available to answer participant questions as needed. Peers will maintain a log of peer contact, which will be submitted to research program staff weekly.

Peers will have access to drug treatment clinic staff for support with trouble shooting any arising matters.

Peers will submit weekly logs of participant contact to the research program coordinator and meet as a group (both peers and research program coordinator at each site, either virtually or in person) to review best practices and address any issues or questions related to effective performance as a peer.

If the participant does not want to work with the assigned peer, they can choose not to receive peer services.

HCV treatment initiation. At the treatment initiation visit, if still eligible for the study after all Day 0 results are available (detectable HCV RNA, platelet count >150,000, not pregnant) the patient will be offered immediate initiation of HCV treatment.

HCV treatment will be initiated at the drug treatment center. Participants will be provided a 4-week supply of glecaprevir/pibrentasvir (GLE/PIB) combination. For patients who report living and other situations that pose barriers to safe storage of a 4-week supply of medications, individual drug treatment centers will develop processes for providing GLE/PIB in quantities that can be safely stored by the participant.

At the treatment initiation visit, participants will be given a follow up appointment for 8 weeks after treatment initiation (expected end of treatment) with designated drug treatment center staff.

Standard of Care Referral to Offsite Location: Participants randomized to standard of care arm will be referred to an offsite HCV treatment site.

Using a signed release of medical information form, research staff will follow up with the referral site to see if the patient scheduled and subsequently attended an appointment and collect information on subsequent progress along the HCV care continuum.

If the patient is confirmed to have scheduled the appointment, study staff will contact the evaluating physician to make them aware that the study may provide GLE/PIB for HCV treatment.

Participants in the standard of care arm who do not initiate HCV treatment within 6 months (24 weeks) after randomization and still meet study eligibility criteria upon rescreen will be offered HCV treatment at the OTP site via rollover to the Intervention Arm.

Any participant that does not clear HCV infection will be linked to repeat HCV treatment and care at an offsite HCV treatment location through standard of care. There are approved regimens available to treat patients who do not achieve cure with first line treatment.

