7.2 Definition for Analysis Populations

All analyses will be conducted with a modified intention to treat approach, which excludes randomized participants who were found on testing to have an undetectable HCV RNA, HBsAg positive or a platelet count <150,000.

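### The on-site treatment check in 4.2.9 does not match the removal rule in 4.2.8 or the mITT exclusions in 7.2 and 7.3.2, so a few participants barred from on-site treatment can stay in the primary analysis

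*Combined protocol and SAP*

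**What the plan says.** Three rules bear on a participant whose Day 0 results come back after randomisation.

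- **Who leaves the study (4.2.8 Randomization):** "Participants who are found to have an HCV RNA that is not detectable, HbsAg positive or a platelet count that is <150,000 will not continue". Pregnancy is not on this list, although the same section says that several Day 0 results, ending with "and urine/serum beta HCG, may not be available at the time of randomization and participants may be randomized without this information".
- **Who is offered on-site treatment (4.2.9 Study Arms):** the offer is made "if still eligible for the study after all Day 0 results are available", and the parenthesis that follows reads "detectable HCV RNA, platelet count >150,000, not pregnant". HBsAg is not named.
- **Who is analysed (7.2, repeated in 7.3.2):** the mITT approach "excludes randomized participants who were found on testing to have an undetectable HCV RNA, HBsAg positive or a platelet count <150,000". Pregnancy is not named.

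Two other sections matter. Section 4.2.5 says "Pregnant women will not be enrolled in this study". Section 5.1 requires "Negative pregnancy test at screening or at the day of treatment initiation (females of childbearing potential only") and lists a positive HBsAg and platelets below 150,000 as exclusions. The primary endpoint (3.2) is the proportion starting HCV treatment within 12 weeks of randomisation.

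**The concern.** The mITT set drops participants after randomisation. That is defensible when the dropped groups are defined by baseline samples and match the rule that decides whether a person can be treated under the protocol. Here the two rules differ. Someone can be barred from on-site treatment by the protocol and still be analysed as a participant whom the strategy failed to start on treatment. That lowers the observed initiation rate for a reason unrelated to how well test and treat works.

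The plan also leaves such cases to be settled one at a time, in an open-label trial of 124 with allocation known. A complete rule fixed in advance avoids that. Finally, the list read at the treatment-initiation visit differs from the eligibility criteria, and a site form copied from it would not prompt for HBsAg.

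**Working it through.** **1. The lists side by side**

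| Day 0 result | 4.2.8: leaves study | 4.2.9: fails the on-site check | 7.2 and 7.3.2: out of mITT |
|---|---|---|---|
| HCV RNA undetectable | yes | yes | yes |
| HBsAg positive | yes | not named | yes |
| Platelets below 150,000 | yes | yes | yes |
| Platelets exactly 150,000 | no | yes (must exceed 150,000) | no |
| Pregnancy test positive | not named | yes | not named |

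Sections 4.2.8, 7.2 and 7.3.2 match, and only 4.2.9 departs. Two rows produce a participant who fails the on-site check but stays in the analysis: a positive pregnancy test and a count of exactly 150,000. The HBsAg row does not, because those participants are removed and excluded from analysis.

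**2. Can the pregnancy case arise?** Section 4.2.5 bars enrolment of pregnant women and allows a point-of-care test. But 4.2.8 lists beta HCG among results that may be pending at randomisation, and 5.1 accepts a test on the day of treatment initiation. So it can arise.

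**3. Reproducing the plan's sample size.** Inputs from 7.1 and 7.3.1: 70% against 40%, two-sided alpha 0.05, power 85%, about 10% dropout.

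- Uncorrected: n₀ = [1.960·√(2·0.55·0.45) + 1.036·√(0.21 + 0.24)]² / 0.30² = 47.8, so 48 per arm.
- Continuity-corrected: n = (n₀/4)·[1 + √(1 + 4/(n₀·0.30))]² = 54.3, so 55 per arm.
- Dropout: 55/0.90 = 61.1, so 62 per arm and 124 in total.

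Power at n per arm, continuity-corrected: Φ{[d − 1/n − 1.960·√(2p̄(1−p̄)/n)] / √[p₁(1−p₁)/n + p₂(1−p₂)/n]}, where d = p₁ − p₂ and p̄ is their mean. At n = 55 this is Φ{[0.300 − 0.0182 − 1.960·0.0949]/0.0905} = 85.5%, which matches the stated 85%. The uncorrected value is 89.6%, so the corrected formula is the right baseline here.

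**4. Effect of affected participants.** The documents give no count. *Assumption:* k = 1, 2 or 3 per affected arm, all non-initiators, among 55 (1.8%, 3.6%, 5.5%). In an affected arm the expected rate becomes p·(55 − k)/55.

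| k | Both arms affected: rates | Difference | Power | Intervention arm only: rates | Difference | Power |
|---|---|---|---|---|---|---|
| 0 | 70.0% v 40.0% | 30.0 | 85.5% | 70.0% v 40.0% | 30.0 | 85.5% |
| 1 | 68.7% v 39.3% | 29.5 | 83.9% | 68.7% v 40.0% | 28.7 | 81.9% |
| 2 | 67.5% v 38.5% | 28.9 | 82.3% | 67.5% v 40.0% | 27.5 | 77.8% |
| 3 | 66.2% v 37.8% | 28.4 | 80.6% | 66.2% v 40.0% | 26.2 | 73.3% |

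Differences are in percentage points, taken before the rates were rounded.

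**The case against.** Four objections deserve an answer.

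- **The parenthesis in 4.2.9 is shorthand.** It is governed by a condition of continuing eligibility and omits other 5.1 criteria too. This stands for HBsAg. A reader might infer that an HBsAg-positive participant could be treated on site, or is counted as a failure. Neither follows: 4.2.8 and 5.1 bar such a participant, and 7.2 excludes them from analysis. The objection does not help with pregnancy, where 4.2.9 names a criterion that the removal and analysis rules lack.
- **The dilution need not favour one arm.** A reader might infer a bias against the intervention arm, because the check sits in the on-site pathway. That would require referral-arm participants with the same result to start treatment elsewhere within 12 weeks. The documents do not say whether off-site clinicians would treat them, and 4.2.5 and 5.1 cover both arms. One-arm dilution is possible but not established.
- **Keeping randomised participants in the analysis is not an error in itself.** This is correct. It is closer to full intention to treat and, if it biases at all, does so toward no effect. But this plan has already chosen to exclude by baseline result, so the exclusion rule should be complete and match the operational rule.
- **Numbers will be small.** This is likely, given the point-of-care test and the Figure 2 note that laboratory samples may be taken before randomisation. Three cases among 55 is a rate that nothing in the documents supports.

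**Conclusion.** There is a real inconsistency between 4.2.9 and the rules in 4.2.8, 7.2 and 7.3.2. Its analytic consequence is confined to a pregnancy found after randomisation and, almost trivially, a platelet count of exactly 150,000. The omission of HBsAg from 4.2.9 is a drafting inconsistency and not permission to treat.

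On the assumed one to three cases, power falls by 1.6 to 4.9 points if both arms are affected alike, and by 3.6 to 12.2 points if only the intervention arm is. These ranges rest on the assumed counts and on scoring affected participants as non-initiators. That scoring follows from the binary endpoint, but no section states it. The upper end of the one-arm range needs both an unlikely count and treatment of all such referral-arm participants at the usual rate. The stated sample size and power are reproduced and need no change. Severity: minor.

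**What to change.** Reconcile 4.2.8, 4.2.9, 5.1, 7.2 and 7.3.2 to a single list of disqualifying Day 0 results, with the platelet boundary written the same way throughout. Refer to that list for continuation in the study, for the on-site treatment offer and for mITT exclusion. For the analysis set, base exclusion on samples taken at Day 0, whenever the result is reported, and apply it identically in both arms, so that nothing occurring after randomisation decides who is analysed. Which clinical criteria and thresholds belong on the list is for the sponsor to decide.

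The cost is wording in five sections, a matching change to any eligibility form built on them, and possibly a few fewer analysed participants.
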